The effects of LLLT on tooth movement were studied in both clinical and animal studies. Numerous human studies have shown that LLLT can simulate the velocity of tooth movement. At that point, it is emphasized that the effects of laser application on bio simulation is dose dependent. ⁽¹³⁾

By reviewing the available Literature , little studies demonstrated the acceleration of orthodontic tooth movement by aligner associated with LLLT , so the goal of the

present study is directed to evaluate the rate of correction of lower incisor crowding by clear aligner and LLLT versus clear aligner alone .

Aim of the study :

The present study will be performed to evaluate the effect of low-level laser therapy (LLLT) on the rate of orthodontic tooth movement through the correction of lower incisors crowding using clear aligners .

Subjects and methods :

Patients with lower anterior mild to moderate crowding will be collected from AlAzhar University from Faculty of Dental Medicine for Girls and post records will be collected after relieve of crowding .

Study design: Randomized Control Study.

Randomization will be done by using Microsoft Office Excel 2007 . patients information will be entered into a computer ,then the computer randomly assigns the patients to two groups that helping to prevent bias.

Control group (n=11) patients will receive a conventional therapy with clear aligners and the investigational group (n=11) will receive the new treatment therapy by using clear aligners for the treatment of mild to moderate lower anterior crowding with laser acceleration .

Sample size calculation⁽¹⁴⁾:

This power analysis used leveling and alignment improving % as the primary outcome. Based upon the results of . AlSayed Hassan MMAA et al (7102); the mean (Standard deviation) values were 89.42 (7.16) and 71.7 (16.18) %, respectively. The effect size (d) was 1.416. Using alpha (α) level of (5%), β level of 0.8 (Power = 80%); the minimum estimated sample size was 9 subjects per group. Sample size was increased to 11 subjects per group to compensate for a dropout rate of 20% after 6 months. Sample size calculation was performed using G*Power version 3.1.9.2.

Ethical approval:

The research protocol approved by ethical committee of Faculty of Dental Medicine, girls, Al-Azhar University, (P-OR-22-05). The steps of the procedure will be explained to the patients / parents and an informed consent will be signed

Inclusion criteria⁽¹⁵⁾:

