1. A well-behaved, compliant, and motivated patient.
2. Patients from 16 to 23 years old .
3. Patients with mild to moderate anterior lower crowding.
4. Full complement of teeth (except for wisdom teeth).
5. Class I Angle malocclusion .

Exclusion criteria⁽¹⁶⁾:

1. Patients with missed anterior teeth .
2. Class II or III Malocclusion (dental or skeletal) .
3. Any systemic diseases that may interfere with assigned treatment plan .
4. Periodontal affection especially at lower anterior teeth .

Method:

Each patient will have the following record taken before the delivery

:

- Orthodontic casts (upper and lower).
- Photography, both intraoral and extraoral ○ lateral cephalometric X-ray .
- Panoramic X-ray

Treatment groups:

The sample will be divided into two groups according to laser application, 11 patients each group :

Group (A): Clear aligners will be used to treat patients with lower anterior crowding with low level laser acceleration .

Group (B): Clear aligners will be used to treat patients with lower anterior crowding without laser acceleration .

Statistical analysis :

Measurements will be taken and the collected data will be tabulated and analyzed statistically.

References:

1. **Das P. J. , Dkhar W. , Pradhan A.** . An Evaluation of Dental Crowding in Relation to the Mesiodistal Crown Widths and Arch Dimensions in Southern Indian Population . *JCDR*.2017;11:01-3.
2. **Jaber S. T., Hajeer M. Y., Burhan A. S. & Latifeh, Y.** . The Effect of Treatment With Clear Aligners Versus Fixed Appliances on Oral Health-Related Quality of Life in Patients With Severe Crowding: A One-Year Follow-Up Randomized Controlled Clinical Trial .*cureus* .2022;14: 1-26.
3. **Nüser C. , Jung K. , Helms H. J. , Engelke W. , Sandoval P.** .Interaction between deglutition, tongue posture, and malocclusion: A comparison of intraoral compartment formation in subjects with neutral occlusion or different types of malocclusion . *Angle Orthod*. 2016 ;86:697-705 .
4. **Tamer I. , Öztaş E. , Marşan G.** . Orthodontic Treatment with Clear Aligners and The Scientific Reality Behind Their Marketing: A Literature Review . *TurkJOrthod*.2019;32:741-6 .
5. **Hennessya J. , Garveyb R. S. , Al-Awadhib E. A.** . A randomized clinical trial comparing mandibular incisor proclination produced by fixed labial appliances and clear aligners . *Angle Orthod* .2016;86:706-12 .

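### The available text describes no masking of whoever measures crowding, so the primary outcome could be read by someone who knows the arm

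*Combined protocol and SAP*

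**What the plan says.** The trial is labelled "Study design: Randomized Control Study", with no mention of blinding or masking. Under 'Treatment groups', Group A is described as "Clear aligners will be used to treat patients with lower anterior crowding with low level laser acceleration" and Group B as "Clear aligners will be used to treat patients with lower anterior crowding without laser acceleration". No sham laser is described.

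The one remark about bias, under 'Study design', is that "the computer randomly assigns the patients to two groups that helping to prevent bias".

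The primary outcome is named only under 'Sample size calculation': "This power analysis used leveling and alignment improving % as the primary outcome". No crowding index or measuring method is defined, so taking crowding as the thing measured is an inference from the stated aim. The whole of 'Statistical analysis' reads: "Measurements will be taken and the collected data will be tabulated and analyzed statistically".

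The 'Method' section lists upper and lower casts, photographs and X-rays among the records taken before delivery. On final records, 'Subjects and methods' says that "post records will be collected after relieve of crowding". It gives no criterion for relief and does not say who decides.

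**The concern.** Randomisation protects the comparison up to the moment of assignment. It does nothing for a measurement made months later by someone who may know which patients had laser. The plan's background is favourable to laser, so a reader who knows the arm would have an expectation in one direction. With no index, instrument or repeat-reading check defined, nothing else in the text limits the reader's discretion.

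At stake is the false-positive rate of a trial with 11 patients per arm. A systematic reading difference between arms adds directly to the estimated treatment effect, and no later analysis can separate the two. Masked reading therefore has to be arranged before the records are measured.

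**Working it through.** **Inputs, all from 'Sample size calculation'.** Means (SD) of 89.42 (7.16) and 71.7 (16.18) %; d = 1.416; alpha 5%, sidedness not stated; power 80%; 9 per group, raised to 11 for dropout.

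**The plan's own figure.**
- Planned difference = 89.42 − 71.7 = 17.72 points.
- Pooled SD = √((7.16² + 16.18²)/2) = √((51.27 + 261.79)/2) = 12.51.
- d = 17.72/12.51 = 1.416, as stated.
- A two-sample t-test (noncentral t, two-sided 5%) has power 0.750 at 8 per group and 0.805 at 9. The stated 9 is reproduced, which supports reading the 5% as two-sided.

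**Sensitivity to a reading shift.** The documents give no reading error, so the shift b is an assumption. Take no true effect and a systematic between-arm difference of b points. The chance of a significant result is the noncentral-t rejection probability with df = 2n − 2 and noncentrality b/(SD × √(2/n)). Solving for the b that raises this from 5% to 10% gives:

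| SD used | 9 per arm | 11 per arm |
|---|---|---|
| 7.16 (smaller arm SD) | 2.34 | 2.09 |
| 12.51 (pooled) | 4.09 | 3.65 |
| 16.18 (larger arm SD) | 5.29 | 4.72 |

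As a fraction of 17.72:
- Pooled SD: 4.09/17.72 = 23% and 3.65/17.72 = 21%.
- Across both arm SDs: from 2.09/17.72 = 12% to 5.29/17.72 = 30%.

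**One assumed example, b = 5 points.** With the pooled SD the false-positive rate is 12.5% (9 per arm) or 14.5% (11 per arm). Across the two arm SDs it runs from 9.5% to 28.6% (9 per arm) and from 10.6% to 34.5% (11 per arm).

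**Unequal SDs together.** A simulation giving one arm an SD of 7.16 and the other 16.18, with shifts of 4.09 (9 per arm) and 3.65 (11 per arm), rejects in 10.9% and 10.6% of trials with the pooled t-test, and in 9.8% and 9.7% with the Welch test. The result does not depend on equal variances.

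Bias in when the final record is taken is not quantified; the documents give nothing to base it on.

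**The case against.** The strongest reply is that this is silence in a very short plan, not a documented decision to read outcomes unmasked. That stands. Part of the document was not available for review, so the point is an omission in the text that was. A reader might infer that outcomes will be measured unmasked, or that the result will be biased. The documents support neither.

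Second, open arms do not in themselves unmask a reader. The missing sham concerns the patient and the operator, and nothing in the documents suggests that a dental cast reveals whether laser was used. This also stands: reading bias arises only if the measurer learns the arm some other way, such as by treating the patient. The text does not rule that out.

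Third, the scale may not transfer. The SDs and the 17.72-point difference come from a cited study. If both arms are recorded once crowding is relieved, improvement may be high in both by construction, and the information would lie in the time taken. That would fit the stated goal to "evaluate the rate of correction of lower incisor crowding by clear aligner and LLLT versus clear aligner alone". This limits what the figures can bear: they show how sensitive a trial of this size is, not how much bias to expect. It is also tempting to quote only a fifth to a quarter of the planned difference. That range rests on the pooled SD alone; the two arm SDs widen it to 12% to 30%.

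Fourth, if timing drives the rate of correction, the undefined point of relief may matter at least as much as the reading. That is fair, but it is a separate weakness that coding cannot repair, and it does not remove the reading gap.

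**Conclusion.** The concern holds as an omission. The available text describes no masking, no coding of records and no sham, and its only bias control concerns assignment. It therefore permits the primary outcome to be read by someone who knows the arm; whether that would happen, and how large any shift would be, is unknown.

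Under a two-sided 5% t-test and no true effect, the shift that doubles the false-positive rate is 3.7 to 4.1 points with the pooled SD, and 2.1 to 5.3 points across the plan's two arm SDs. Both the SDs and the planned difference are borrowed and may not hold for records taken at relief. The safeguard should be added: a modest shift would matter at this sample size, and the remedy is inexpensive.

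**What to change.** Add to 'Statistical analysis' wording such as:

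*The pre- and post-treatment records used for the outcome will have name, date and group replaced by a random code, assigned by a study team member who does not measure. Records will be mixed across arms and measured in code order without access to the allocation. The code will be broken only after the measurements are locked.*

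If masked reading is already intended, this simply records it.

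**Cost.** An existing team member relabels the outcome records of 22 patients, and measurement is done in a batch rather than as patients finish. Crowding must already be judged at enrolment, because severity is an inclusion criterion, and again at relief, so the coded reading is probably a second measurement. No new patients, visits or procedures are needed. Masking will be incomplete if the measurer also treats patients and recognises some cases.

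**What it leaves open.** Coding does not address arm knowledge affecting when the post records are taken. The report should state as a separate limitation that these records are triggered by relief of crowding, with no stated criterion or decision-maker.
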